12.5 Summary of Efficacy Endpoint Analyses

Efficacy Endpoint	Collection Time	Method
Primary		
Relative change from Baseline in SALT score to	Baseline and Week 24	Descriptive statistics by visit and dosing regimen with difference in means and two-sided 90% CI (t-distribution) for each post-baseline visit
Week 24		 Main analysis: using LOCF imputation based on mITT analysis population
		 Supportive analysis: using LOCF imputation based on PP analysis population, if applicable
		 Subgroup analyses: using LOCF imputation based on mITT analysis population within each subtype of alopecia areata at Baseline
Secondary		
Responder (90%, 75% and 50%) in relative change from Baseline in SALT	Baseline and Weeks 4, 8, 12, 16, 20, and 24	Count and proportion of subjects by visit and dosing regimen for each responder definition separately with difference in proportions and two-sided Wald 90% CI for each post-baseline visit
score at Weeks 4, 8, 12, 16, 20, and 24	6,	 Main analysis: using LOCF imputation based on mITT analysis population
		 Supportive analysis: using LOCF imputation based on PP analysis population, if applicable
		 Subgroup analyses: using LOCF imputation based on mITT analysis population within each subtype of alopecia areata at Baseline

	STATISTICAL ANALYSIS PLAN, Final v1.0
Protocol Number CP543.2003	Sponsor: Concert Pharmaceuticals, Inc.

Efficacy Endpoint	Collection Time	Method
Absolute change from Baseline in SALT score to	Baseline and Week 4, 8, 12, 16, 20, and 24	Descriptive statistics by visit and dosing regimen with difference in means and two-sided 90% CI (t-distribution) for each post-baseline visit
Weeks 4, 8, 12, 16, 20, and 24		 Main analysis: using LOCF imputation based on mITT analysis population
		 Supportive analysis: using LOCF imputation based on PP analysis population, if applicable
		 Subgroup analyses: using LOCF imputation based on mITT analysis population within each subtype of alopecia areata at Baseline
Relative change from Baseline in SALT score to Weeks 4, 8, 12, 16, and 20 Baseline and Week 4, 8, 12, 16, and 20	· · · · · · · · · · · · · · · · · · ·	Descriptive statistics by visit and dosing regimen with difference in means and two-sided 90% CI (t-distribution) for each post-baseline visit
		 Main analysis: using LOCF imputation based on mITT analysis population
	 Supportive analysis: using LOCF imputation based on PP analysis population, if applicable 	
	 Subgroup analyses: using LOCF imputation based on mITT analysis population within each subtype of alopecia areata at Baseline 	
Change from Baseline in satisfaction of hair coverage to Week 24	Baseline and Week 24	Descriptive statistics by visit and dosing regimen with difference in means and two-sided 90% CI (t-distribution) for each post-baseline visit
		• Main analysis: with no imputation based on mITT analysis population
		 Additional analysis: shift from baseline (satisfied vs. dissatisfied) to each post-baseline visit with no imputation based on mITT analysis population
		No supportive and subgroup analyses

	STATISTICAL ANALYSIS PLAN, Final v1.0
Protocol Number CP543.2003	Sponsor: Concert Pharmaceuticals, Inc.

Efficacy Endpoint	Collection Time	Method
Exploratory		
Change from Baseline in VAS for Eyebrows to Week 24	Baseline and Week 24	Descriptive statistics by visit and dosing regimen for each eyebrow separately with difference in means and two-sided 90% CI (t-distribution) for each post-baseline visit
		• Main analysis: with no imputation based on mITT analysis population
		No supportive and subgroup analyses
Change from Baseline in satisfaction of hair	Baseline and Week 24	Descriptive statistics by visit and dosing regimen with difference in means and two-sided 90% CI (t-distribution) for each post-baseline visit
coverage quality to Week		• Main analysis: with no imputation based on mITT analysis population
24		No supportive and subgroup analyses
Other		
Responder (80%) in relative change from Baseline in SALT score at	Baseline and Weeks 4, 8, 12, 16, 20, and 24	Count and proportion of subjects by visit and dosing regimen for each responder definition separately with difference in proportions and two-sided Wald 90% CI for each post-baseline visit
Weeks 4, 8, 12, 16, 20, and 24		 Main analysis: using LOCF imputation based on mITT analysis population
		• Supportive analysis: using LOCF imputation based on PP analysis population, if applicable
		• Subgroup analyses: using LOCF imputation based on mITT analysis population within each subtype of alopecia areata at Baseline

	STATISTICAL ANALYSIS PLAN, Final v1.0
Protocol Number CP543.2003	Sponsor: Concert Pharmaceuticals, Inc.

Efficacy Endpoint	Collection Time	Method
Proportion of subjects with a SALT score of ≤ 10 and ≤ 20 , at Weeks 12, and 24	Week 12, and 24	Count and proportion of subjects by visit and dosing regimen for each definition separately with difference in proportions and two-sided Wald 90% CI for each post-baseline visit
		 Main analysis: using LOCF imputation based on mITT analysis population
		 No supportive and subgroup analyses
Proportion of subjects in each CGI-S category at Baseline and Weeks 8, 12,	Baseline and Weeks 8, 12, and 24	Count and proportion of subjects by category, visit, and dosing regimen • Main analysis : with no imputation based on mITT analysis population • No supportive analyses
and 24		 Subgroup analyses: based on mITT analysis population within each subtype of alopecia areata at Baseline
Proportion of subjects in	Weeks 8, 12, and 24	Count and proportion of subjects by category, visit, and dosing regimen
each CGI-I category at Weeks 8, 12, and 24		 Main analysis: with no imputation based on mITT analysis population; distribution of each treatment group across the different categories will be compared using a Chi-square test
		 Additional analysis: Improved vs not improved at each post-baseline visit based on mITT analysis population; subjects with a missing CGI-I at a specific visit will be classified as not improved for that visit and distribution of each treatment group across the different categories will be compared using a Chi-square test at each visit.
		No supportive analyses
		Subgroup analyses: using LOCF imputation based on mITT analysis population within each subtype of alopecia areata at Baseline

	STATISTICAL ANALYSIS PLAN, Final v1.0
Protocol Number CP543.2003	Sponsor: Concert Pharmaceuticals, Inc.

Efficacy Endpoint	Collection Time	Method
Proportion of subjects in each PGI-S category at Baseline and Weeks 8, 12, and 24	Baseline and Weeks 8, 12, and 24	Count and proportion of subjects by category, visit, and dosing regimen • Main analysis: with no imputation based on mITT analysis population • No supportive analyses
and 24		 Subgroup analyses: using LOCF imputation based on mITT analysis population within each subtype of alopecia areata at Baseline
Proportion of subjects in each PGI-I category at Weeks 8, 12, and 24	Weeks 8, 12, and 24	Count and proportion of subjects by category, visit, and dosing regimen • Main analysis: with no imputation based on mITT analysis population; distribution of each treatment group across the different categories will be compared using a Chi-square test
		 Additional analysis: Improved vs not improved at each post-baseline visit based on mITT analysis population; subjects with a missing CGI-I at a specific visit will be classified as not improved for that visit and distribution of each treatment group across the different categories will be compared using a Chi-square test at each visit.
		No supportive analyses
		 Subgroup analyses: using LOCF imputation based on mITT analysis population within each subtype of alopecia areata at Baseline

	STATISTICAL ANALYSIS PLAN, Final v1.0			
Protocol Number CP543.2003	Sponsor: Concert Pharmaceuticals, Inc.			

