#### **11.4.2.** Efficacy

For the primary efficacy endpoint and other continuous measures, the confidence interval(s) for the dosing regimen difference at Week 24 will be calculated. For categorical measures (e.g. proportion of responders), the confidence interval(s) for the dosing regimen difference at Week 24 will be calculated based on normal approximation for the binomial distribution, using the Wald continuity correction [(1/n1 + 1/n2/2]].

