3.3 Randomization, Replacement, and Unblinding Procedures

Patients meeting all inclusion criteria and none of the exclusion criteria will be randomized to 12 mg BID CTP-543 or 24 mg QD CTP-543 in a 1:1 ratio. Randomization will be stratified by classification of alopecia areata subtype into one of the following three categories: 1) alopecia areata, 2) alopecia totalis or alopecia universalis, or 3) alopecia ophiasis.

Patients who withdraw or are withdrawn from the study will not be replaced.

To maintain the blind for investigators, subjects, and site personnel, subjects will take their randomized treatment in the am and pm no matter which regimen they are randomized to. The Clinical Research Organization (CRO) study team will also remain blinded to the dosing regimen until database lock.

The study will be unblinded after approval of the SAP, clinical trial data are entered into the database, any discrepancies in the data are resolved, determination of the inclusion/exclusion of each subject from each analysis population and lock of the database.

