6 STATISTICAL CONSIDERATIONS

6.1 Sample Size

A sample size of 25 patients (completers) per group provides adequate precision for the estimated dosing regimen difference for relative change in SALT score from Baseline at Week 24. Precision of the estimated difference is quantified by the width of the 90% confidence intervals (CI) for the dosing regimen difference.

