6.8 Adjustments for Covariates

Not applicable.

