6.9 Examination of Subgroups

The analysis of the primary and secondary efficacy endpoints will be repeated for the following subgroups (refer to Section 8 for the definition of each alopecia areata subtype):

- Subjects with alopecia areata at Baseline;
- Subjects with alopecia totalis or alopecia universalis at Baseline;
- Subjects with alopecia ophiasis at Baseline

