12 EFFICACY ANALYSIS

12.1 Primary Efficacy Endpoint Analysis

The primary efficacy endpoint is the relative change from baseline in SALT score at Week 24. The SALT is a measure of hair absence that quantifies the amount of scalp surface without hair in a pre-specified quadrant of the scalp (right side [RRS], top [TRS], left side [LRS], and back [BRS]), that is further summed after applying a quadrant-specific multiplier indicative of scalp surface area contribution, to provide an overall score of total hair loss:

Total SALT Score =
$$(LRS * 0.18) + (RRS * 0.18) + (TRS * 0.40) + (BRS * 0.24)$$

Refer to Section 6.2 for an important note about SALT absolute change from Baseline and relative change from Baseline endpoint definitions

Relative change in SALT score from Baseline to Week 24 will be summarized descriptively based on the mITT analysis population by dosing regimen. Difference of the means between the two

	STATISTICAL ANALYSIS PLAN, Final v1.0
Protocol Number CP543.2003	Sponsor: Concert Pharmaceuticals, Inc.

dosing regimens will also be provided along with a two-sided 90% Confidence Interval (CI). SALT data will be displayed in a by-subject data listing.

Line plots of means (+/- standard error of the mean [SEM]) SALT score over time by dosing regimen will be presented. Similar, line plots of means (+/- SEM) absolute change in SALT score and relative change from Baseline in SALT score over time by dosing regimen will also be provided.

Supportive Analysis

If applicable (refer to Section 4.2), the primary efficacy analysis will be repeated based on the PP analysis population.

Subgroup Analyses

Subgroup analyses by Baseline alopecia areata subtype (refer to Section 8 for the definition of Baseline alopecia areata subtype) will be performed.

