12.2 Secondary Efficacy Endpoint Analyses

12.2.1 Responder Analysis: Proportion of patients achieving at least a 90%, 75%, and 50% in relative change from Baseline in SALT score at Weeks 4, 8, 12, 16, 20, and 24

For the proportion of patients achieving at least a 90%, 75%, and 50% relative change from Baseline in SALT score at Weeks 4, 8, 12, 16, 20, and 24, frequency and proportion will be presented by dosing regimen based on the mITT analysis population. The difference in proportions along with the two-sided Wald 90% CI (using the binomial approximation with a Wald continuity correction) will also be provided at each visit.

Additionally, line plots of proportions of patients over time by dosing regimen will be presented for the proportion of subjects achieving ate least a 50% in relative change from baseline only.

The same supportive and subgroup analyses as for the primary efficacy endpoint will be performed for this secondary efficacy endpoint (refer to Section 12.1).

12.2.2 Absolute change in SALT score from Baseline to Weeks 4, 8, 12, 16, 20, and 24, and relative change in SALT score from Baseline to Weeks 4, 8, 12, 16, and 20

For the absolute change in SALT score from Baseline to Weeks 4, 8, 12, 16, 20, and 24 as well as the relative change in SALT score from Baseline to Weeks 4, 8, 12, 16, and 20, a similar analysis approach as outlined for the primary efficacy endpoint (refer to Section 12.1) will be used, including the supportive and subgroup analyses.

	STATISTICAL ANALYSIS PLAN, Final v1.0
Protocol Number CP543.2003	Sponsor: Concert Pharmaceuticals, Inc.

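### Randomisation is stratified by alopecia subtype, but the SALT-change intervals ignore the strata and may be wider than needed

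*SAP*

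**What the plan says.** SAP 3.3 states: "Randomization will be stratified by classification of alopecia areata subtype into one of the following three categories". The categories are patchy alopecia areata, totalis or universalis, and ophiasis. Protocol 6.4 and 8.1 agree, with 1:1 allocation.

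The analysis does not carry the strata through. SAP 6.8 (Adjustments for Covariates) reads only "Not applicable". SAP 12.1 takes the raw difference of the two regimen means with a two-sided 90% interval, and the SAP 12.5 row gives the method as "Descriptive statistics by visit and dosing regimen with difference in means and two-sided 90% CI (t-distribution) for each post-baseline visit". For absolute change, and for relative change at earlier visits, SAP 12.2.2 says that "a similar analysis approach as outlined for the primary efficacy endpoint (refer to Section 12.1) will be used".

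Subtype enters only through SAP 6.9: "The analysis of the primary and secondary efficacy endpoints will be repeated for the following subgroups". On sample size, SAP 6.1 says: "Precision of the estimated difference is quantified by the width of the 90% confidence intervals". It gives no SD and no target width. SAP 6.4 rules out formal hypothesis tests. SAP 3.4, which lists changes from the protocol, does not discuss leaving out the stratification factor.

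**The concern.** Stratified allocation balances the arms on subtype, so differences between subtypes largely cancel out of the estimated regimen difference. The two-sample t-interval does not know this. Its standard error still contains the spread between subtypes. If subtype is prognostic, the stated uncertainty is larger than the true uncertainty, and a nominal 90% interval covers more than 90%.

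What is at stake is precision. This trial has no test, no margin and no target width, and interval width is its only stated yardstick. The subtype repeats in SAP 6.9 give separate estimates within each subtype, not one prespecified stratified overall estimate. Patients who withdraw are not replaced, so lost precision cannot be recovered by enrolling more.

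**Working it through.** **The plan's own figure.** The 25 completers per group cannot be reproduced, because neither document gives an SD or a target width. The unadjusted 90% half-width is t(0.95, 2n−2) × SD × √(2/n). At n = 25 this is 1.677 × 0.283 × SD = 0.474 SD, or 14.2, 16.6, 19.0 and 21.3 points for assumed SDs of 30, 35, 40 and 45. The step from 25 completers to 30 randomised is consistent with a dropout of 1/6.

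**General effect of adjustment at 25 per arm.** Let R² be the share of outcome variance explained by subtype. The width ratio is √(1−R²) × t(0.95, 46)/t(0.95, 48).

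| R² | 0 | 0.05 | 0.10 | 0.20 | 0.30 |
|---|---|---|---|---|---|
| Change in width | +0.1% | −2.4% | −5.1% | −10.5% | −16.3% |

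**Translating this into subtype gaps.** The following are assumptions, not figures from the documents:

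- 60 patients, within-stratum SD σ = 35 points on relative change, and mean response lower by g points in totalis/universalis, with ophiasis responding like patchy disease.
- A mix of 24/32/4 (patchy / totalis-universalis / ophiasis). Protocol 4.4.1 reports a mean baseline SALT of about 88 in the earlier phase 2 study. If SALT is 100 in totalis/universalis and averages 74.5 elsewhere, the totalis/universalis share is (88 − 74.5)/25.5 = 53%.
- A second mix of 11/45/4, at the 75% cap in Protocol 6.3.

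With balanced arms, the variance used by the unadjusted interval is about σ² + N p(1−p) g²/(N−2), where p is the totalis/universalis share. The adjusted interval uses σ². The t multipliers differ by less than 0.1%. At 24/32/4 and g = 20:

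- Unadjusted variance = 1225 + 60 × 0.249 × 400/58 = 1225 + 103 = 1328, so SD = 36.4.
- Ratio = 35/36.4 = 0.96.

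Simulation of 20,000 trials per scenario, 1:1 within stratum and with no regimen effect, agrees:

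| Gap g (points) | 0 | 10 | 20 | 30 | 40 | 50 |
|---|---|---|---|---|---|---|
| Width ratio, 24/32/4 | 1.000 | 0.990 | 0.961 | 0.917 | 0.865 | 0.810 |
| Width ratio, 11/45/4 | 1.002 | 0.993 | 0.971 | 0.937 | 0.895 | 0.847 |
| Width ratio, 20/27/3 (25 per arm) | 1.004 | 0.994 | 0.964 | 0.921 | 0.868 | 0.812 |
| Unadjusted half-width, 24/32/4 | 15.0 | 15.2 | 15.7 | 16.4 | 17.4 | 18.6 |
| Unadjusted coverage, 24/32/4 (%) | 90.0 | 90.3 | 91.4 | 92.7 | 94.2 | 95.7 |

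The adjusted half-width stays at about 15.1 points, with coverage of 89.8–90.1%. In patients, the loss at g = 20 is about 60 × (1 − 0.961²) = 4.6 of 60. At g = 30 it is 60 × (1 − 0.917²) = 9.5.

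**Sensitivity to the SD.** At 24/32/4 and g = 20 the gain is 7.4, 5.2, 3.9, 3.0 and 2.4% for SDs of 25, 30, 35, 40 and 45.

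**Absolute change.** SAP 6.2 makes this relative change × baseline/100. With SALT uniform on 50–99 outside totalis/universalis, and a mean relative change there of 45 or 60, the width change is −0.6% to +0.3% at gaps of 10–20 points. At a gap of 30 it is −2% to −4%.

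**Three levels or two.** If ophiasis responds like totalis/universalis (mix 22/32/6), the three-level model gives a ratio of 0.922 at g = 30. Pooling ophiasis with patchy disease gives 0.949, with coverage of 90.9%. Three levels are therefore preferable while the data allow.

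**Cost if subtype is not prognostic.** Two degrees of freedom cost 0.04% of width at 60 patients and 0.06% at 50. Uneven splits cost more. The information on the regimen difference is Σ n₁n₀/n over strata:

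- 20/27/3, split as evenly as possible: 5 + 6.74 + 0.67 = 12.41, against 12.5 unadjusted. √(12.5/12.41) is about 0.4% wider.
- 24/32/4 with ophiasis 3:1: 6 + 8 + 0.75 = 14.75, against 31 × 29/60 = 14.98; 0.8% wider.
- 24/32/4 with ophiasis 4:0: 6 + 8 + 0 = 14, against 32 × 28/60 = 14.93; 3.3% wider, because those four patients drop out of the comparison.

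**The case against.** The strongest reply is that nothing is wrong. The planned interval is unbiased and conservative, the study is a 60-patient phase 2 trial for estimation only, and no target width is missed. SAP 6.8 is an explicit choice, and subtype is examined in the subgroup repeats. With balance within strata the point estimate is identical, so only the width moves: at a 20-point gap, by about 0.6 points on a half-width of 15.7. The half-width itself varies by about 9% from trial to trial. The SD and gap are assumed, and gains above 10% need gaps of about 40 points, which no passage supports. The mix is inferred from another study: assuming an average SALT of 70 or 80 outside totalis/universalis, instead of 74.5, moves the share to 60% or 40%. Absolute change gains little, and responder intervals would stay unadjusted beside adjusted SALT-change intervals.

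Most of this is correct, and it limits the point to precision. It does not remove it. The mix matters little: at g = 20 the gain is still 3.6% at 34/22/4 and 2.5% at 44/12/4. Random variation in width does not offset a systematic excess. The subgroup repeats do not supply a stratified overall difference. The sponsor considered subtype important enough to stratify on, cap and analyse separately. Set against a cost close to zero, even a modest expected gain favours adjustment.

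**Conclusion.** The concern holds as a recommended improvement. The SAP stratifies the randomisation and leaves the strata out of the SALT-change intervals. If subtype is prognostic, those intervals are too wide and over-cover. Under the stated assumptions (SD 35, mix 24/32/4 or 11/45/4), the excess is about 1% of width at a 10-point gap, 3–4% at 20 points and 6–8% at 30 points. It is zero if there is no gap. For absolute change there is essentially no gain at gaps of 10–20 points. No conclusion of the trial would be made wrong by leaving the plan as it is. The true size cannot be taken from the documents.

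**What to change.** Before unblinding, replace the entry in SAP 6.8 and align 12.1, 12.2.2 and the three SALT-change rows of 12.5 with wording such as:

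> Relative and absolute change in SALT are analysed at each visit with a linear model containing regimen and randomisation stratum as randomised (three levels). If either arm has no ophiasis patient in the analysis population, ophiasis is pooled with patchy alopecia areata. The adjusted regimen difference and its two-sided 90% CI are reported. Raw means and the unadjusted difference with its t-interval are supportive output. The PP repeat uses the same model. Within-subtype repeats (Section 6.9) use the unadjusted difference and t-interval, because the stratum term is constant there.

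The pooling rule prevents the loss from a 4:0 ophiasis split. Baseline SALT is not proposed as a further covariate: the documents do not show that it predicts relative change beyond subtype, and it would cost about 1% of width if it does not. No change is proposed here for the responder intervals, eyebrow VAS or satisfaction.

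The cost is SAP wording and one model term, using a stratum already recorded. No protocol amendment is needed, since Protocol 11.4.2 leaves the method open for continuous measures: "For the primary efficacy endpoint and other continuous measures, the confidence interval(s) for the dosing regimen difference at Week 24 will be calculated".

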13 SAFETY/TOLERABILITY ANALYSIS

All safety/tolerability analyses will be conducted based on the Safety analysis population by dosing regimen. No statistical inferences will be performed on any safety endpoint. All safety endpoints will be listed in by-patient data listings.

13.1 Adverse Events

AEs will be coded according to the MedDRA, version 22.0.

An AE reported after informed consent, but before the first dose of study drug (i.e., Day 1), will be considered a pre-treatment adverse event.

TEAEs are defined as any AEs with onset date/time on or after the first dose of study drug. See Appendix 3 for handling of completely or partially missing dates for AEs. In the case where it is not possible to define an AE as treatment emergent or not, the AE will be classified as treatment emergent.

An overall summary table of AEs will be provided. The frequency and percentage of patients who experienced at least one AE, TEAE, TEAE by greatest relationship with study drug, TEAE by highest severity/intensity, serious TEAE, treatment-related serious TEAE, TEAE leading to study drug discontinuation, TEAE leading to study drug dose interruption, TEAE leading to study discontinuation, and TEAE leading to death will be presented.

Frequency and percentage of patients who experienced TEAE will be summarized by SOC and PT. A patient experiencing multiple TEAEs within the same SOC will be counted only once for that SOC. Similarly, a patient experiencing multiple TEAEs within the same PT will be counted only once for that PT. TEAEs will be sorted alphabetically by SOC and PT will be presented by decreasing order of total frequency within each SOC. Serious TEAEs and treatment-related serious TEAEs will be summarized similarly.

Frequency and percentage of patients who experienced TEAE will be further broken down by greatest relationship to study drug. A treatment-related AE is defined as any TEAE that is assessed by the Investigator as definitely, probably or possibly related to study drug. A not related TEAE is defined as any TEAE that is assessed by the Investigator as unlikely related or not related to the study drug. TEAE with an unknown/missing relationship to study drug will be considered as treatment related. A patient experiencing multiple TEAEs within the same SOC will be counted only once for that SOC under the greatest relationship to study drug. Similarly, a patient

	STATISTICAL ANALYSIS PLAN, Final v1.0			
Protocol Number CP543.2003	Sponsor: Concert Pharmaceuticals, Inc.			

experiencing multiple TEAEs within the same PT will be counted only once for that PT under the greatest relationship to study drug.

Frequency and percentage of patients who experienced TEAE will be further broken down by highest severity (mild, moderate, and severe). TEAE with severity of life-threatening and fatal will be reported under the severe intensity category while TEAE with an unknown/missing severity will be considered as severe. A patient experiencing multiple TEAEs within the same SOC will be counted only once for that SOC under the highest severity. Similarly, a patient experiencing multiple TEAEs within the same PT will be counted only once for that PT under the highest severity.

Listings of all AEs, all AEs leading to death, all serious AEs, all TEAEs leading to study drug discontinuation and all TEAEs leading to study discontinuation will be provided.

